8.1 Session Information/Preparation

Site coordinators at the three accrual sites will communicate to each other the number of subjects being assigned to a group as they are randomized to the Intervention arm. When the group enrollment gets to six, they will close enrollment to that group and begin enrolling in the next group. Coordinators will slow enrollment if needed so that subjects are not enrolled in a group starting more than 2 months from the enrollment date. If needed, the team will discuss adding additional groups to the schedule on different dates so that subjects will be able to start within the 2-month window from enrollment date.

For intervention session schedules, the protocol will include two different schedules for intervention session administration. This design is to provide flexibility for participants and also to maximize study accrual and participation. The schedules include:

Schedule #1: Two sessions administered on the same day, with a break in between. There will be a 4-week interval between the first set of 2 sessions and second set of 2 sessions. The caregiver session will be held two weeks after the first set of sessions.

Schedule #2: One session administered per day, once a week over a five-week period. There will be a one-week interval between session 2 and session 3 during which the caregiver session will be held.

The two schedules vary throughout the study period based on participants' convenience and preference.

If a subject misses a session, they can make up just the missed session with the next 1 or 2 scheduled groups rather than start over with a new group. If they miss both Session 1 and Session 2, they can be re-assigned to the next group as long as the next group size doesn't

exceed 6, or at the ostomy nurses' ([name] and [name]) discretion if the group size would exceed 6.

If a subject misses Session 3 or Session 4 or both, they can make up the missed session(s) with the next 1 or 2 scheduled groups. If they miss both chances to make up the sessions, they will be asked to do the surveys and will be analyzed as a separate group using an intent-to-treat contrast.

To account for making up sessions or delays in completing interim surveys, for both intervention and usual care groups, the 6-month followup surveys will be requested from subjects 6 months after the date the interim surveys are completed.

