12.0 STATISTICAL CONSIDERATIONS

12.1 General. Aim 1 will be analyzed with linear mixed models for repeated measures. Aim 2 will utilize a variety of sources and methods to enumerate the intervention program and ostomy-related family resources in each study arm.

If a subject misses Session 3 or Session 4 or both, they can make up the missed session(s) with the next 1 or 2 scheduled groups. If they miss both chances to make up the sessions, they

will be asked to do the surveys and will be analyzed as a separate group using an intent-to-treat contrast.

12.2 Aim 1: Using our enhanced telehealth techniques, determine if **patient activation**, self-efficacy, ostomy-related knowledge, and HRQOL will be improved and sustained over time in the online interactive communication Ostomy Self-Management Telehealth program (OSMT) curriculum compared to a UC group.

Under an intent-to-treat approach, change in outcomes will be evaluated longitudinally with linear mixed models, testing the effect of study arm adjusted for potential confounders. Such models evaluate both associations and rates of change, accounting for within-subject correlation. The Primary Outcome will be PAM. Secondary Outcomes include SE, COH-QOL-CRC scales, and Ostomy Knowledge. Post hoc contrasts will evaluate effect of training (baseline to post) and whether effect is sustained after training (6 month post to follow-up). Standard multivariable modeling procedures will be used to select or eliminate potential confounding variables, starting with candidate variables that are biologically plausible or found to be associated with endpoint change scores (baseline vs. follow-up) in bivariate analyses with a p-value of less than 0.20. Potential candidate covariates and confounders include (but are not limited to) CG participation in training sessions, depression (HADS), time since surgery, ostomy type, age, sex, stage, anticipated permanence of ostomy, and pre- or post-surgical radiation or chemotherapy. We will explore potential interaction for plausible effect modifiers, such as gender, or having a CG.

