12.13 Sample Size and Power. Total potential sample size 240 (up to 120 per arm), to ensure at least 75 per arm completing the study with complete baseline COH-QOL-CRC scaled items, assuming a 15% dropout rate. This will maintain sufficient power for the COH-QOL-CRC scaled items. The larger sample size for the primary endpoints Patient Activation Measure (PAM) and ostomy management self-efficacy (SE) will provide 80% power to detect a 2.75 change in PAM and a 0.50 change in SE, which is not considered excessively powered. Detectable differences based on variances observed from our R21 for PAM and SE, as well as from our R01 for COH-QOL-CRC subscales. We changed two items slightly on the self-efficacy questions to make them ostomy-relevant. Our observed variation for ostomy management SE is consistent with the original form of symptom management SE across different patient samples reported by Lorig's group (SD range 2.1 to 2.4).⁵¹⁻⁵⁷ We will examine the reliability of these items and expect them to have a Cronbach's alpha of ≥ 0.75 . Calculated detectable differences were based on the following assumptions 1) alpha of 0.05, 2) within-subject correlation on repeated measures of 0.60. Estimates are based on repeated measures multivariable modeling, adjusted for baseline,

with two follow-up measurements. Also shown for comparison are two rough indices of clinically important differences. Sufficient research has not been performed on these scales to determine with certainty a minimal clinically-important difference that is anchored on participant self-assessment of health status. An alternative suggested by Sloan⁵⁸ is the empirical rule effect size (ERES) method to judge minimally important differences (MID) in outcome measures. We also present 50% of the observed sample SD, a common rule-of-thumb for clinically meaningful differences.⁵⁹ The table shows that even with substantial shortfall in sample size (down to 65 per group) we still can detect differences below the estimated MID.

Detectable Outcome Differences with 80% Power						
Measure	SD	N= 75	N=70	N=65	ERES⁵⁸	.5 SD⁵⁹
Patient Activation Measure	13	3.4	3.5	3.6	8.0	6.5
Ostomy self-management self-efficacy	2.3	0.60	0.62	0.64	0.80	1.2
COH-QOL-CRC Total	1.6	0.42	0.43	0.45	0.88	0.8
COH-QOL-CRC Physical	1.8	0.47	0.49	0.51	0.88	0.9
COH-QOL-CRC Psychological	1.8	0.47	0.49	0.51	0.88	0.9
COH-QOL-CRC Social	2.1	0.55	0.57	0.59	0.88	1.1
COH-QOL-CRC Spiritual	2.2	0.57	0.59	0.62	0.88	1.1

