**Statistical Analysis Plan**

## Statistical Analysis Plan

**General.** Aim 1 will be analyzed with linear mixed models for repeated measures. Aim 2 will utilize a variety of sources and methods to enumerate the intervention program and ostomy-related family resources in each study arm.

**Aim 1:** Using our enhanced telehealth techniques, determine if **patient activation**, self-efficacy, ostomy-related knowledge, and HRQOL will be improved and sustained over time in the online interactive communication Ostomy Self-Management Telehealth program (OSMT) curriculum compared to a UC group.

Under an intent-to-treat approach, change in outcomes will be evaluated longitudinally with linear mixed models, testing the effect of study arm adjusted for potential confounders. Such models evaluate both associations and rates of change, accounting for within-subject correlation. The Primary Outcome will be PAM. Secondary Outcomes include SE, COH-QOL-CRC scales, and Ostomy Knowledge. Post hoc contrasts will evaluate effect of training (baseline to post) and whether effect is sustained after training (6 month post to follow-up). Standard multivariable modeling procedures will be used to select or eliminate potential confounding variables, starting with candidate variables that are biologically plausible or found to be associated with endpoint change scores (baseline vs. follow-up) in bivariate analyses with a p-value of less than 0.20. Potential candidate covariates and confounders include (but are not limited to) CG participation in training sessions, depression (HADS), time since surgery, ostomy type, age, sex, stage, anticipated permanence of ostomy, and pre- or post-surgical radiation or chemotherapy. We will explore potential interaction for plausible effect modifiers, such as gender, or having a CG.

The COH QOL-CRC assesses ostomy burden and care abilities, including time taken to perform daily ostomy care, comfort with ostomy care, comfort with diet, adjustment of diet for ostomy, appetite, clothing and other problems with ostomy placement. We will also measure clinically related outcomes, including medical attention for problems with bowel, bladder, or ostomy. Changes in these responses will be compared between treatment groups with linear mixed models, chi-square tests or t-tests, as appropriate.

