Descriptive statistics will be presented on attendance at training sessions. We will describe and contrast quantity and type of ostomy-care help (professional and lay) sought outside of the training sessions, including calls for support from study Peer Ostomates. Self-reported Peer Ostomate call frequency and duration will be corroborated with a call log maintained by the Peer Ostomate. We will evaluate hypothesized association between OSMT attendance level and outcomes using linear mixed models that have a weighted attendance score as an independent variable. Alternative attendance scores will be tested that give weight to ostomy-care help outside of training sessions.

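### The protocol's rule that late non-attenders in the OSMT arm form a separate group leaves it unclear whether they count in OSMT for the primary PAM comparison

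*Protocol*

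**What the plan says.** Protocol 8.1 gives OSMT participants who miss Session 3, Session 4 or both a chance to catch up with either of the next two scheduled groups. Of those who still do not attend, it says "they will be asked to do the surveys and will be analyzed as a separate group using an intent-to-treat contrast". Protocol 12.1 repeats the rule: they "will be analyzed as a separate group using an intent-to-treat contrast". Neither section says what is contrasted with what.

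Protocol 12.2, which follows directly, sets the primary analysis of PAM as an intent-to-treat mixed model "testing the effect of study arm adjusted for potential confounders". The SAP repeats this: "Under an intent-to-treat approach, change in outcomes will be evaluated longitudinally with linear mixed models". The SAP also carries over the opening paragraph of 12.1, but not the missed-session rule. It handles partial attendance through descriptive statistics and through mixed models with a "weighted attendance score as an independent variable".

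For the first two sessions, 8.1 gives only logistics. A single missed session can be made up, and "If they miss both Session 1 and Session 2, they can be re-assigned to the next group". No analysis rule is attached, so those participants fall under the general intent-to-treat statement.

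**The concern.** Intent-to-treat keeps each participant in the randomised arm. This rule forms a group from behaviour after randomisation. Usual care (Protocol 9.1) has no sessions, so the group has no usual-care counterpart.

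Read plainly, the rule takes late non-attenders out of OSMT. The primary PAM test would then set the rest of OSMT against all of usual care, and randomisation would no longer protect the comparison. Because the rule stands in the general part of the statistical section, just before the primary analysis, an analyst could take it as an exception to that analysis. Nothing says which statement governs. If the choice is left open until the data are seen, it could be made with knowledge of the result.

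**Working it through.** **Possible readings of the rule**

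| Reading | OSMT in the primary PAM test | Consistent with 12.2 and the SAP? |
|---|---|---|
| Set apart from OSMT | OSMT without its late non-attenders | No |
| Supplementary contrast beside the main analysis | All randomised to OSMT | Yes |
| Separate level, recombined with the rest of OSMT against usual care | All randomised to OSMT | Yes |

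Only the first changes the primary comparison. The rest of this section shows what it could do.

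**Inputs from Protocol 12.13.** PAM SD 13; alpha 0.05 (sidedness not stated, two-sided assumed); "within-subject correlation on repeated measures of 0.60"; two follow-ups adjusted for baseline; at least 75 completers per arm; 80% power; half an SD is 6.5 points.

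**Step 1: reproduce the plan's figure.** Detectable difference = 13 × (1.96 + 0.842) × √(2f/n), where f is the variance factor.
- f = (1 − 0.60²)/2 = 0.32 gives 3.36, 3.48 and 3.61 at n = 75, 70 and 65. The table has 3.4, 3.5 and 3.6, so this is the factor that matches. It treats the two follow-ups as independent given baseline.
- f = (1 + 0.60)/2 − 0.60² = 0.44 is the usual factor for the baseline-adjusted mean of two follow-ups with equal correlations. It gives 3.95 at n = 75.

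Both factors are used below; the point does not depend on the choice. Standard errors at 75 per arm are 13 × √(2 × 0.44/75) = 1.408 and 13 × √(2 × 0.32/75) = 1.201.

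**Step 2: assumptions not in the documents.** The share m set apart is 10% or 20% of OSMT. Their raw PAM gap from the rest of OSMT is 6.5 points. If that gap is already present at baseline, adjustment leaves 6.5 × (1 − 0.60) = 2.6 points. If it opens after baseline, adjustment does not reduce it and it stays at 6.5.

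**Step 3: formulas.**
- Bias = m × adjusted gap.
- Type I error, if they do worse regardless of treatment = P(|Z + bias/SE| > 1.96).
- Power at a true 3.4 points, if they do better = Φ((3.4 − bias)/SE − 1.96).

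Example (20%, 2.6 points, f = 0.32): bias = 0.20 × 2.6 = 0.52; 0.52/1.201 = 0.433; type I error = P(Z > 1.527) + P(Z < −2.393) = 6.3% + 0.8%, or 7.2% before rounding the parts.

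**Step 4: results.** Each pair is f = 0.44 / f = 0.32.

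| Share | Adjusted gap | Bias | Type I error, SE at 75 v 75 | Type I error, OSMT reduced to 75(1 − m) | Power at 3.4 if they do better, SE at 75 v 75 |
|---|---|---|---|---|---|
| none | – | 0 | 5.0 / 5.0% | – | 67.5 / 80.8% |
| 10% | 2.6 | 0.26 | 5.4 / 5.5% | 5.4 / 5.5% | 60.6 / 74.4% |
| 20% | 2.6 | 0.52 | 6.6 / 7.2% | 6.4 / 6.9% | 53.4 / 66.9% |
| 10% | 6.5 | 0.65 | 7.5 / 8.4% | 7.3 / 8.2% | 49.7 / 62.9% |
| 20% | 6.5 | 1.30 | 15.2 / 19.1% | 14.0 / 17.5% | 32.0 / 41.6% |

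The reduced-arm column uses SE = 13 × √(f × (1/(75(1 − m)) + 1/75)). Against the 3.4-point detectable difference, the bias runs from 0.26/3.4 = 8% to 1.30/3.4 = 38%. With no gap there is no bias.

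**The case against.** The strongest reply is that the primary analysis is already settled. Protocol 12.2 and the SAP both call for an intent-to-treat test of study arm. The SAP has no exception, so read alone it keeps these participants in OSMT. The rule itself names intent-to-treat and keeps collecting their surveys, which fits retaining them. Partial attendance has its own planned models. On this view the rule describes an extra contrast, and dropping these participants is the reading that fits the surrounding text least well.

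Much of this stands, and it rules out several stronger readings that a reader might infer:
- **That the protocol excludes these participants from the primary test.** It does not say so, and two of the three readings keep them in.
- **That the rule contradicts itself.** A rule with coherent alternative readings is ambiguous. The conflict with 12.2 arises only on the plain reading.
- **That the SAP's silence is a further defect.** The silence favours intent-to-treat.
- **That OSMT completers would be compared with all of usual care.** The rule covers only Sessions 3 and 4, so people who missed earlier sessions would remain in the OSMT group.

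The reply does not remove the ambiguity. The protocol nowhere calls the contrast supplementary, nor says that these participants also stay in the primary model.

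**Conclusion.** The point holds as an unresolved question about who is in the OSMT arm for the primary PAM comparison. It should be fixed. That the rule is present and its contrast undefined is certain. Harm is conditional: it needs the plain reading to be followed, enough people to be set apart, and a PAM gap between them and the rest of OSMT.

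The documents give neither that share nor that gap, so they fix neither the size nor the direction of bias. People who miss late sessions may be doing worse or better than the others. A reader might infer that the rule favours OSMT; the documents do not support that. With 10–20% set apart and an adjusted gap of 2.6–6.5 points, type I error is about 5.4–19% if they do worse regardless of treatment (5.4–17.5% once the smaller OSMT arm is allowed for). The lower values belong to a gap already present at baseline, the higher ones to a gap that opens later. If they do better, the cost is power. These figures illustrate the mechanism and are not estimates for this trial.

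**What to change.** In Protocol 8.1 and 12.1, keep the request to complete the surveys. Remove the words "will be analyzed as a separate group using an intent-to-treat contrast" and the conjunction before them, and add:

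*All randomized participants, whichever sessions they attend, miss or make up, will be analyzed in the arm to which they were randomized for the primary and secondary arm comparisons. Any separate analysis of participants who miss Session 3 and/or 4 and both make-ups is supplementary.*

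Put the same text in the SAP, beside the attendance-score models already planned. If the supplementary analysis is wanted, say what is compared with what. This keeps the option of examining late non-attenders and settles the arm comparison for everyone, including those who miss earlier sessions.

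The cost is one clause replaced in two protocol sections and two sentences added to the SAP. Surveys are already requested from these participants, so no extra data are needed. The change should be made before any comparison between arms is seen.

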8.1.1 Telehealth Connection Information (Appendix 8)

8.1.2 Group Rules (Appendix 9)

8.1.3 Goal Setting (Appendix 10)

Participants will receive the four-page goal setting form (Appendix 10) as part of the patient packet mailed to them before the first session, and will be asked to list goals for helping improve their daily life prior to Session 1 (page 1 of the form). Their goals will be discussed during Session 1 and will be revisited and possibly revised in Session 2 (page 2 of the form) and again in Session 3 (page 3 of the form). Participants should be instructed to keep a copy of the first page of the form and return the completed first page with the baseline surveys. Participants should be instructed to return page 2 after Session 2, and return page 3 after Session 4 along with the interim surveys. The final page 4 should be returned with the followup surveys six months after the end of the sessions. Site Coordinators will key in goal setting data for data entry.

8.2 Surveys (Appendices 2 to 7)

8.2.1 Baseline surveys to be completed are:

1. COH-QOL-CRC (full survey; Appendix 2a AND Appendix 2b)
2. HADS (Appendix 3)
3. PAM (Appendix 4)
4. Self-Efficacy (Appendix 5)
5. Ostomy Knowledge (Appendix 6)
6. Burden of Care (full survey; Appendix 7a [NOTE: **Do not include** Greatest Challenge portion of Appendix 7a])
7. Goal Setting (page 1 of 4; Appendix 10)

8.2.2 End of Session surveys to be completed are:

1. COH-QOL-CRC (43 scaled items only; Appendix 2b)

2. HADS (Appendix 3)
3. PAM (Appendix 4)
4. Self-Efficacy (Appendix 5)
5. Ostomy Knowledge (Appendix 60)
6. Burden of Care (short form; Appendix 7b)
7. Goal Setting (pages 2 and 3 of 4; Appendix 10)

8.2.3 6-month Follow-up surveys to be completed are:

1. COH-QOL-CRC (43 scaled items only; Appendix 2b)
2. HADS (Appendix 3)
3. PAM (Appendix 4)
4. Self-Efficacy (Appendix 5)
5. Ostomy Knowledge (Appendix 6)
6. Burden of Care (full survey; Appendix 7a [NOTE: **Include** Greatest Challenge portion of Appendix 7a])
7. Goal Setting (page 4 of 4; Appendix 10)

8.2.4 **RedCap® Surveys.** Surveys will be available to complete electronically via the web in RedCap, which will be preferred administration method unless subjects cannot manage the method or express a strong preference against it. The UA Data Core will provide each medical center with a list of survey ID's linked to subject IDs. The survey ID's allow the subject to log into the RedCap survey and can only be used once. Medical centers will provide each subject with the survey link and his or her survey ID at the appropriate time for each of the three survey periods.

8.2.5 **Survey Tracking.** Survey/Participant status will be tracked using an MS Access tracking database maintained at UA Data Core, with mirror databases at each medical center for their respective samples. However, the medical center tracking database will account for all potentially eligible participants, whereas the UA Data Core tracking database will only contain consented subjects. Since paper surveys are returned to respective sites, whereas RedCap surveys are transmitted to UA Data Core, the disposition of consented subjects in the master tracking database will be synchronized with the medical center tracking databases on a weekly basis.

8.2.6 **Survey Follow up.** Telephone contact with respondents will be initiated under four circumstances: 1) for non-respondents (paper survey not returned or RedCap survey not submitted within 2 weeks of mailing or provision of RedCap survey ID); 2) when a returned survey has incomplete or illegible data; 3) when the respondent has questions or requests a call; and 4) if a HADS score is 11 or greater on the depression questions (Appendix 3), the coordinator will inform the participant that this might indicate depression and they should see their physician. This will be documented as a memo in their study file. This will be done within 24 hours of receiving the survey. This will not preclude their participation.

8.2.7 **Returned Survey Processing.** Paper questionnaires returned will be logged in the medical center tracking system. This includes packets returned as "undeliverable, no forwarding address," which would generate a phone call to subject to clarify mailing address. RedCap questionnaires submitted to UA RedCap server will be logged into the Data Core tracking system. Returned paper questionnaires will be stored securely in a locked office or filing cabinet. Each questionnaire will be reviewed for missing responses, improperly marked

responses, handwritten comments on the survey forms, and inserted letters and notes from respondents.

8.2.8 Cleaning PHI. Any comments that reveal PHI will be masked before photocopying paper questionnaires and destroyed in the case of RedCap surveys.

8.2.9 Missing Items. All surveys will be reviewed for completeness based on the criteria outlined below. If the respondent appears to have inadvertently skipped questions, the interviewer will contact the respondent by telephone and attempt to complete the missing items. Unusual situations should be brought to a study project meeting to discuss issues before contacting participant. Use the following guidelines to determine how to handle missing items:

- a. Make all decisions of intent based on marginal notes first (i.e., fill in the answers not bubble filled, but indicated by a written note)
- b. Appropriately skipped questions based on skip patterns will not be counted as missing.
- c. Call backs will be placed when the following criteria are met:
 - i. Full page is missing
 - ii. >20% questions missing (or more than 1 response to choose best answer questions), not counting open-ended questions, appropriately skipped questions, or sensitive area questions listed below
 - iii. The following sensitive questions will not be counted in determining need for callback, nor asked during a call back if missing:
 1. COH-QOL-CRC intimacy item “Has your ostomy interfered with your ability to be intimate?”
 2. COH-QOL-CRC spiritual item “Is support you receive from personal spiritual activities such as prayer or meditation sufficient to meet your needs?”
 3. COH-QOL-CRC religious item “Is support you receive from religious activities such as going to church or synagogue sufficient to meet your needs?”
 4. COH-QOL-CRC Sexual activity items.
 5. COH-QOL-CRC race/ethnicity items
 6. COH-QOL-CRC household income item
 7. Open ended questions will not be counted towards a call back or asked in a callback.
- d. If the participant declines to answer a question again during the call back, initials will be placed by the question and the question will be left blank.

8.2.10 Shipping paper surveys to Data Core. Hard copy surveys will be reviewed for PHI, which will be masked if present, and scanned to a PDF file within a secure server at each site. These PDF files will be uploaded into RedCap, using a built-in application called Send-It, in which files stay behind the RedCap firewall until retrieved by intended RedCap user recipient from the same RedCap project. Files can only be downloaded by the designated recipient, and that recipient must have log-in capability to RedCap and assignment to the specific project. Within RedCap on the “My Projects” page (one level up from the PCORI project), there is a tab on the right called “Send-it” with an envelope icon. Instructions within the tab are clear to follow. Each PDF file should have only one subject and one event (baseline, interim, followup). Files should be named according to a consistent naming convention for each site based on subject ID number and event (e.g., 1001 baseline.pdf; 2003 followup.pdf, etc.). Data Core staff will download PDF files from Send-it to a secure University of Arizona server and key data responses into the RedCap database. PDF files will be deleted at end of the study.

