3	Discuss completed assignment. Content promotes a healthy lifestyle via nutritional management, physical activity recommendation and overcoming barriers, psychological health, and improving attitudes. Participants are encouraged to set new priorities, evaluate friends, and work on changing negative attitudes. Tips for traveling are included. Discussion includes potential ostomy complications. Assignment: Review personal goals in regards to ostomy care.
4	Booster Intervention content driven by group demands and needs. The CG will also be invited to this session to help ensure a well-rounded understanding of issues, comfort with ostomy care, and anticipated future dilemmas. Discuss attainment of personal goals for participation in OSMT.

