9.5 Survey Plan

We will survey HRQOL to measure short term (at the end of Session 4) and long term (6 months) sustainability for all participants.

Baseline – see 8.1

End of Sessions – Surveys will be mailed if requested one day following the last session or instructed on RedCap

6 month follow-up – Surveys will be mailed if requested one day following the last session or instructed on RedCap

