3. Skin Adhesive Removers
 - a. Used to remove adhesive after applying the wafer and pouch (Not recommended for routine use)
 - b. Some ostomates find it easier to reapply wafer if some adhesive is left on the skin
4. Deodorizers
 - a. Used to reduce odor
 - b. Tablet form you eat or drop into pouch
 - c. Vents are also available to apply to pouch to release gas and deodorize it as it passes through the vent
5. Stoma Patches and Caps
 - a. Used to prevent leakage when colostomy is irrigated and stool is controlled
 - i. Pouch Covers: A cover that goes around your pouch to absorb sweat and to cover the contents of the pouch

- ii. Convexity
 - a) Skin irritation can occur from leakage on the skin
 - b) Use of convex wafer makes the stoma protrude from skin and redirects flow of urine or feces into pouch
- 6. Pouches
 - a. One Piece System
 - i. The wafer and pouch are attached as one unit
 - ii. Advantages
 - a) Quick and easy to use
 - b) Less Bulky (One vs. Two Parts)
 - b. Two-Piece System
 - i. The wafer and pouch are two separate pieces and are attached by attaching the wafer connector to the pouch connector
 - ii. Advantages
 - a) Can change bag size for different moments
 - b) Easier to relieve gas
 - iii) Disadvantage
 - a) Since attached wafer to bag, error may occur causing leakage
 - b) May be difficult to attach wafer to pouch and abdomen if ostomate is visually impaired
- 7. Belts
 - a. Some ostomates prefer to wear a belt
 - i. Attach to wafers using a special tag
- 8. Daily Care
 - a. Colostomy bag should be emptied when reaches 1/3 gas or stool
 - i. Achieve pouch adherence up to 5 days
 - b. If you use the reusable pouches, make sure they are thoroughly cleaned with mild soap and water
- 9. Disposal of ostomy bag
- 10. Reviewing Routines
- 11. Emergency Kits

Session 1 Assignments (5 min)

C. Assignments

1. Goal Development for Session 2

When you completed the first survey packet, it contained a goal development sheet. We are now going to ask you to please describe the goals you have in regards to your ostomy care.

2. Monitoring timed daily outputs/Nutrition Log by Time

Please monitor your daily bowel movements and how they are affected by different situations or foods. These will be discussed at upcoming sessions and will be useful if issues were written down.

Session 1 Resources (5 min)**D. Resources**

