15.10 Appendix 10 Goal Setting

PATIENT GOAL SETTING FORM

(Keep a copy for discussion in Session 1 and complete online or return this first page with initial surveys)

Participant ID: _____

Date: _____

Intervention Nurse: _____

Goals for Ostomy Care and Daily Living

What are three goals to help improve your daily life in the next month in the context of your ostomy, either related to the ostomy and ostomy care, or daily living in general, or both?

Examples of potential goals might be: *To apply an ostomy bag so no leakage occurs; To explore dietary changes that will not lead to ostomy-related problems; To travel with more confidence in ostomy care; To participate in (special and/or routine) family activities/celebrations; To participate more in social activities (dining out, attending parties, meeting new people, enjoying music/theater/sports/hobbies/other entertainment).*

1. _____

2. _____

3. _____

PATIENT GOAL SETTING FORM

(Complete online or return this after Session 2 is completed)

Participant ID: _____

Date: _____

Intervention Nurse: _____

Session 1/Session 2 - Please evaluate the progress in achieving each goal from last session. Use only one circle for each goal.

	Goal Achieved		Goal Ongoing		Goal No Longer Necessary	
Goal 1	Yes	No	Yes	No	Yes	No
Goal 2	Yes	No	Yes	No	Yes	No
Goal 3	Yes	No	Yes	No	Yes	No

List three goals for the next month. You may include the same goals or add new goals.

1. _____

2. _____

3. _____

PATIENT GOAL SETTING FORM

(Complete online or return this page with other surveys after Session 4)

Participant ID: _____

Date: _____

Intervention Nurse: _____

Session 3/Session 4 - Please evaluate the progress in achieving each goal from last sessions.

	Goal Achieved		Goal Ongoing		Goal No Longer Necessary	
Goal 1	Yes	No	Yes	No	Yes	No
Goal 2	Yes	No	Yes	No	Yes	No
Goal 3	Yes	No	Yes	No	Yes	No

List three goals for the next 6 months. You may include the same goals from the previous sessions, or add new goals.

1. _____

2. _____

3. _____

PATIENT GOAL SETTING FORM

(Complete online or return this page with 6-month follow-up surveys)

Participant ID: _____

Date: _____

Intervention Nurse: _____

Follow-up - Please evaluate the progress in achieving each goal since last sessions.

	Goal Achieved		Goal Ongoing		Goal No Longer Necessary	
Goal 1	Yes	No	Yes	No	Yes	No
Goal 2	Yes	No	Yes	No	Yes	No
Goal 3	Yes	No	Yes	No	Yes	No

Thank you for participating in this program.

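### Read literally, Protocol 8.2.1 to 8.2.3 send the Goal Setting form to both arms, although other sections treat goal setting as OSMT content

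*Protocol*

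**What the plan says.** Protocol 8.2 gives one list of instruments per survey round. The seventh entry is "Goal Setting (page 1 of 4; Appendix 10" at baseline, "Goal Setting (pages 2 and 3 of 4; Appendix 10" at the end of sessions, and "Goal Setting (page 4 of 4; Appendix 10" at six months. None of the three lists is limited to an arm, and there is no separate usual-care list.

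The survey rounds belong to both arms. Section 7.2.5 pays intervention and usual-care subjects alike for all three. Section 8.1 times the six-month request in the same way for both groups. Section 8.2.4 has the centers give every subject a survey link and ID at each round. Section 9.5 describes the plan as "We will survey HRQOL to measure short term (at the end of Session 4) and long term (6 months) sustainability for all participants".

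Elsewhere the form belongs to the intervention. Section 8.1.3 sits under session preparation. It mails the form ahead of Session 1 and has the goals worked on in Sessions 1 to 3. Section 9.2.4 has participants list goals before Session 1, and the Session 4 description says "Discuss attainment of personal goals for participation in OSMT". The six usual-care elements in 9.1 do not mention goals.

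**The concern.** Goal setting is one of the working parts of a self-management program. Page 1 of Appendix 10 asks "What are three goals to help improve your daily life in the next month in the context of your ostomy" and supplies example goals. Later pages ask the participant to rate progress and to set goals for the next month and then the next six months.

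The primary outcome is patient activation, and self-efficacy is among the secondary outcomes in 12.2. Setting and rating ostomy goals could plausibly move both. If controls do this as well, part of the intervention reaches the comparison group, and any benefit they draw from it narrows the difference that the trial is meant to estimate. Nothing is gained in return, because neither section 11 nor the SAP uses goal data.

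**Working it through.** The question is which arm receives a form, so no arithmetic applies. I set the passages side by side.

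1. **Where the form is listed.** Goal Setting appears in 3 of the 3 survey lists in 8.2. None of the 3 names an arm. None of the 6 usual-care elements in 9.1 mentions goals.

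2. **Whether session wording limits a list to OSMT.** It does not. The 8.2.2 list is named for the end of the sessions, yet it is also the only list under which usual care can give its post-intervention PAM, self-efficacy and quality-of-life data. A coordinator therefore has to apply it to usual care and finds nothing there that removes item 7. The authors did write an exclusion into these lists where they wanted one: item 6 at baseline leaves out the greatest-challenge question. Item 7 carries no such note.

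3. **Which pages are exposed.**
   - Pages 2 and 3 ask for progress ratings tied to session pairs, and page 4 asks for progress since the last sessions. A usual-care participant would find these hard to answer.
   - Page 1 has no ratings. Its instruction line mentions Session 1 and it has a field for the intervention nurse, but the task itself can be done by anyone with an ostomy.

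4. **How page 1 travels.** Section 8.1.3 puts the form in a pre-session packet but has page 1 returned with the baseline surveys. The Session 1 script says "When you completed the first survey packet, it contained a goal development sheet". That line is addressed only to OSMT attendees, so it does not show what usual care receives. It does show that page 1 travels with the baseline survey packet.

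5. **Timing.** Section 7.2.3 places the baseline assessment after consent, and 7.2.2 places randomization after consent. Neither gives the order of the two. If baseline comes first, the arm is not yet known and page 1 in the baseline packet would go to everyone. If baseline comes second, the packet could be split by arm, but 8.2.1 does not tell staff to do so.

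6. **Result.** The lists that staff would follow deliver the form to both arms. Sections 8.1.3, 9.1 and 9.2.4 and the Session 4 description imply that it is for OSMT only. The passages conflict and need to be reconciled.

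**The case against.** The strongest reply is that the form is plainly OSMT material and that item 7 is only a return checklist for people who already hold it. The evidence for this is real. The section heading is "8.2 Surveys (Appendices 2 to 7", and the goal form is Appendix 10, outside that range. Section 8.1.3 places the form beside the telehealth instructions and group rules. The pages refer to sessions and an intervention nurse that usual care does not have. This supports a view of what the authors intended, but it does not change what the lists tell a coordinator to send.

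A reader might go further and infer that usual-care participants do set and review goals throughout the trial. The documents do not support that. No sentence says that they receive the form, and none says that they do not. RedCap settings are not described.

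A reader might also try to turn the exposure into a loss of power by assuming that the form carries some fraction of the OSMT effect. The documents give no such fraction, and a form completed alone, without nurse, peer or group discussion, may do little. The base for the calculation is also unsettled: 12.13 gives a detectable PAM difference of 2.75 for the larger sample and 3.4 at 75 per arm. I therefore give no power figure.

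**Conclusion.** The point holds as an inconsistency with a possible effect on the trial's contrast. Followed as written, 8.2.1 to 8.2.3 give usual care an exercise that the protocol elsewhere treats as intervention content. The firmest exposure is page 1 at baseline; pages 2 to 4 are less likely to be completed by controls because of their session wording.

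The direction, if there is an effect, is toward no difference between arms on PAM and self-efficacy. This assumes that usual-care participants receive and complete the form and that it helps them. The documents support neither a size nor a claim that it has happened. The change is still worth making because it costs almost nothing and removes a doubt about the primary comparison.

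**What to change.** - In 8.2.1 to 8.2.3, remove item 7 from the common lists or mark it 'OSMT arm only'.
- In 8.1.3, state that Appendix 10 goes only to OSMT participants, after randomization, in the pre-session packet, and that page 1 is returned separately from the common baseline packet.
- Change the matching line in the Session 1 script, and the return instruction printed at the head of page 1, to agree.
- Set RedCap so that the form does not open for usual-care survey IDs.
- For any survey round already run, check whether goal pages came back under usual-care IDs and report the count.

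The first four changes cost a few words and one RedCap setting; the check is a short look-up. Goal data from OSMT participants are still collected, and no planned analysis is lost.
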